7.9.1 Primary Objective

The primary objective require development of risk-prediction models for various endpoints using different data source combinations. This section describes a general framework that will be used to develop these models.

Prediction models

For each endpoint, two types of prediction modeling will be considered: one focusing on short term predictions and other on long term predictions. For both prediction modelling types, the following machine learning (ML)/artificial intelligence (AI) methods might be considered (but not limited to):

- Tree Boosting
- Temporal Convolutional networks feedforward neural network (TCN FFNN) (similar approach presented in Catling & Wolff (2020))

Dataset split

DEFINE AFib Statistical Analysis Plan Revision [2.0] Page 14 of 25 Medtronic

Predictive modelling requires the original data to be split into three smaller sets, one for training, one for validation and one for testing. The original data will be randomly split into those three datasets with 70%, 10% and 20% of patients in the training, validation, and testing datasets, respectively. A patient will only contribute data to one of the 3 datasets. To reduce impact of possible heterogeneity across sites, patients and LINQ model, randomization will be stratified by sites, LINQ indication, and LINQ model. Lastly, the testing dataset will only be used after the models under consideration have been trained and validated.

Data format

All predictive models will be trained using similar labeled examples. In particular, at a prediction time point **t** a patient **i** generates a labeled example (hereinafter referred as sliding window) which will be composed of the all features considered as relevant to the clinical endpoint (e.g. LINQ device data, EHR data, etc.) collected between **(t-b)** and **t**, and a binary label indicating if that patient had the clinical event of interest between time points **t+l** and **(t+l+w)**. Figure 1 illustrates the sliding window concept at time **t**. Notice a patient will provide multiple sliding windows.

[figure not shown]

Figure 1: A sliding window at time t is composed of all relevant features values observed from the most recent b days and a binary label indicating if event occurred between t+l and t+l+w. The rationale of the parameter l is to give leading time to the physicians to prevent an event for a patient with high risk of having that event between t+l and t+l+w

Data transformations

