All continuous variables will be centered and scaled. Categorical variables will be converted to into one-hot vectors.

Handling missing data

[figure not shown]
Due to the various types of data sources, handling missing data will depend on the requirements of the predictive model and on the data missing patterns observed in the training data. Thus, the decision on

DEFINE AFib Statistical Analysis Plan Form Medtronic Revision [2.0] Page 15 of 25

the methods to be used for handling missing data will be left to the discretion of the statistician/data scientist during the model development phase. However, this decision will be made prior of using the testing data.

Undersampling/Oversampling

Likely the training dataset will have many more instances (i.e. sliding windows) where a clinical event is not observed. Thus, random undersampling/oversampling methods might be needed to build the training dataset. Notice that these approaches will **not** be used to build the validation and test datasets.

DEFINE AFib Statistical Analysis Plan Form Medtronic Revision [2.0] Page 16 of 25

Training model

All models under consideration will be training with the goal of minimizing the cross-entropy loss function.

Tuning

Hyperparameters b, I and w will be determined via grid search algorithm using the validation set and the Area Under Receiver Operating Characteristic (AUROC) curve as the metric to be maximized. Finite set of reasonable values for b, I and w will be set during the exploratory data analysis.

The tuning approach for hyperparameters associated with the training model process (e.g. number of epochs, batch size, learning rate, optimizer, etc.) will be left to the discretion of the statistician/data scientist.

Testing

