After all models have been trained and tuned, all final models (i.e. for each clinical endpoint and prediction modeling strategy) will be fitted to the testing dataset resulting in a prediction of each patient's individual probabilities of having the clinical event in the predictive window (i.e. between t+l and t+l+w). More specifically, all models will generate risk prediction (for the clinical event they were designed to predict) for each patient at each day (starting at the bth). The true binary values and the corresponding prediction risk scores will be used to compute the area under the receiver operating characteristic (AUROC), sensitivity, specificity, negative predictive value (NPV) and positive predictive value (PPV). Bootstrapping will be used to compute 95% CIs for these performance metrics.

For each outcome, the performance of the risk prediction models will be presented in contrast to the performance of comparable clinical practices. However, as a guideline, the following scale might be used to help choose the adjective to refer the performance of each model:

AUROC ≤ 0.5: fail

DEFINE AFib Statistical Analysis Plan Form Medtronic Revision [2.0] Page 17 of 25

0.5 < AUROC ≤ 0.6: poor

0.6 < AUROC ≤ 0.7: fair

[figure not shown]
0.7 < AUROC ≤ 0.8: good

[figure not shown]
0.8 < AUROC ≤ 0.9: great

[figure not shown]
AUROC > 0.9: excellent

[figure not shown]
Determination of Subjects/Data for Analysis

Subjects in the full analysis set who have completed all enrollment surveys will be included in the primary objective analysis. Subject follow up might be limited by lack of device information.

[figure not shown]

[figure not shown]

DEFINE AFib Statistical Analysis Plan Form Medtronic Page 20 of 25 Revision [2.0]

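### SAP 7.9.1 lets validation AUROC choose the lead time and window that define the predicted outcome; fix one pair per model type in advance

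*SAP*

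**What the plan says.** All of the following is in SAP 7.9.1 unless noted.

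- **Prediction models.** Two types are planned for each endpoint, "one focusing on short term predictions and other on long term predictions". Neither is given a horizon in days.
- **Data format and Figure 1.** Each sliding window carries features from the last b days and "a binary label indicating if event occurred between t+l and t+l+w". The text gives l a clinical purpose: "The rationale of the parameter l is to give leading time to the physicians to prevent an event".
- **Tuning.** "Hyperparameters b, I and w will be determined via grid search algorithm using the validation set", with AUROC as the metric to maximise. The capital I printed there is the l of the label definition. No candidate values are listed: "Finite set of reasonable values for b, I and w will be set during the exploratory data analysis".
- **Dataset split.** Patients are divided 70/10/20 into training, validation and test sets, and "the testing dataset will only be used after the models under consideration have been trained and validated".
- **Testing.** AUROC, sensitivity, specificity, PPV and NPV are computed for the chosen window and set against comparable clinical practice. An optional verbal grading follows: "the following scale might be used to help choose the adjective to refer the performance of each model". Its cut-points do not depend on l or w.

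The only window given in days is the five days before an event used in the retrospective sample-size work (SAP section 6, CIP 13.1). Section 7.9.1 does not adopt it. CIP 13.3.1 tests no hypothesis and sets the goal as a model accurate enough for clinical use.

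**The concern.** Tuning compares candidates against one target. Here b is a legitimate tuning parameter, because changing it alters the features and leaves the outcome alone. Changing l or w changes the outcome itself. A search that ranks (l, w) pairs by AUROC therefore compares scores for different questions.

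AUROC also has no term for lead time, which is the reason the SAP gives for having l. A pair with little warning and high discrimination beats a pair with usable warning and lower discrimination, whatever physicians would need.

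No type I error rate is at stake. What is at stake is which question the primary model answers, and how its performance is then described on a scale that ignores the horizon.

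**Working it through.** **1. The plan's own figures.** 80/0.05/10 = 160 and 80/0.02/10 = 400 events; doubled, 320 and 800. AF-related: 0.21 × 5,000 = 1,050, and 525 if half the cohort gives complete data. Follow-up: 5.2 million / 5,000 = 1,040 days per patient. All reproduce, and none depends on l or w. The 10% validation set would hold about 105 AF-related events, or about 52.

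**2. The outcome changes with w.** With a constant rate of 1,050 / 5.2 million = 0.000202 per day, the share of positive labels is 1 − exp(−rate × w): 0.14% at w = 7, 0.60% at 30, 1.80% at 90 and 7.1% at 365 days. PPV and NPV therefore refer to different quantities across candidate windows.

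**3. AUROC changes with l and w.** This is an illustrative simulation; the process and grids are assumptions.
- Daily log-burden = patient mean + autoregressive process (coefficient 0.97).
- Daily event hazard is log-linear in burden (coefficient 1), with recurrences allowed. The intercept is set so that 21% of patients have an event in 1,040 days.
- Within/between-patient SDs: 1.5/0.5 (time-varying), 1.0/1.0 (mixed), 0.5/1.5 (stable).
- Score = mean log-burden over the last b days, b in {1, 7, 30}. No machine-learning model is trained.
- Short grid: l and w in {7, 14, 30}. Long grid: l in {30, 60, 90}, w in {90, 180, 365}.

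AUROC at the best b for each pair (two cohorts of 5,000 per scenario):

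| Scenario | (7,7) | (30,30) | (30,90) | (90,365) |
|---|---|---|---|---|
| Time-varying | 0.793 | 0.648 | 0.599 | 0.550 |
| Mixed | 0.803 | 0.740 | 0.727 | 0.707 |
| Stable | 0.860 | 0.851 | 0.851 | 0.843 |

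On the SAP scale the short-term contrast reads *good* against *fair*, *great* against *good*, and *great* for both. No long-term contrast changes its adjective. Three fresh cohorts per scenario gave, for (7,7) against (30,30), 0.79–0.80 against 0.63–0.65, 0.79–0.81 against 0.72–0.74, and 0.86–0.87 against 0.84–0.85.

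**4. What the search picks.** The search took the maximum over the 27 (b, l, w) cells in 150 validation sets of 500 patients (mean 106 with an event) and 150 of 250 patients (mean 53). Each grid has nine (l, w) pairs, so chance is 1/9 = 11%.

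| Scenario | Short grid picks (7,7): 500 / 250 patients | Long grid picks (30,90): 500 / 250 patients |
|---|---|---|
| Time-varying | 100% / 97% | 91% / 79% |
| Mixed | 98% / 91% | 61% / 47% |
| Stable | 65% / 56% | 43% / 33% |

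The stable row is fragile. Three fresh cohorts gave 68–75% and 55–60% for (7,7). A further single cohort gave (7,7) in only 11 of 30 draws at each size, and there (90,365) led the long-term search.

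**5. Direction is not fixed.** With the 1.5/0.5 SDs and the hazard driven by burden 21 days earlier, AUROC at w = 7, b = 7 was 0.829, 0.860 and 0.767 for l = 7, 14 and 30. The short-term search chose (14,7) in 95% (500 patients) and 91% (250) of runs.

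**6. Different assumptions.** A fixed true risk score (stable trait plus fluctuating state; about 1,050 events in 5,000 patients over 1,040 days) was scored against several pairs:

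| State SD, trait SD, memory | (0,1) | (0,7) | (0,30) | (7,30) | (30,30) |
|---|---|---|---|---|---|
| 1.2, 0.5, 10 days | 0.792 | 0.724 | 0.627 | 0.587 | 0.548 |
| 1.2, 0.5, 30 days | 0.820 | 0.790 | 0.728 | 0.697 | 0.622 |
| 0.8, 0.8, 10 days | 0.769 | 0.754 | 0.699 | 0.681 | 0.665 |

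Across each row the score is identical and only the outcome definition changes.

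**The case against.** The best defence is that an open horizon suits a development study. The objective asks whether device data can predict AF-related utilisation and names no horizon. Section 7.9.1 calls itself a general framework, and section 7.8 allows revision after the interim analysis. Finding where the signal predicts, then testing it in untouched patients, is a legitimate aim. If *reasonable* in the Tuning paragraph is read in light of the stated purpose of l, every grid cell could be clinically acceptable. Stating a minimum l, or tabulating AUROC by horizon, would also help.

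The size can be contested too:
- The headline contrast takes opposite corners of an assumed grid. Neighbouring cells differ less: in one repeat run, (7,7) against (7,14) was 0.778 against 0.758, 0.802 against 0.792, and 0.864 against 0.861.
- The mixed-case change from *good* to *great* rests on 0.803 against a cut-point of 0.80. The SD of that AUROC across validation samples was about 0.017 (500 patients) and 0.029 (250).
- The simulation matches 21% of patients with an event, not 1,050 events. With recurrences, one repeat run had about 1,257, 1,376 and 1,968.
- The adjectives are optional. The SAP's main reading is relative to clinical practice, and the effect on that contrast was not estimated.

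These points limit the size, and they stand. They do not remove the fault. No safeguard states a horizon for the primary models, and none makes AUROCs computed on different labels comparable. The five-day retrospective window is not carried forward. An early, narrow grid would shrink the problem but still leave discrimination to choose the outcome.

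**Conclusion.** The concern holds. It follows from the SAP text alone: l and w define the label, l has a stated clinical purpose, and both are chosen by a metric blind to that purpose. It should be fixed. It does not threaten the validity of the test-set estimate for the chosen window.

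The consequence in this study cannot be predicted. Under the assumed process and grids, the window alone moved short-term AUROC by 0.145 (time-varying), 0.063 (mixed) or 0.009 (stable), and long-term AUROC by 0.049, 0.020 or 0.008. If risk is mostly stable between patients, the effect is negligible and the selected pair is largely noise. If care lags AF, the search can favour a longer l. Confidence is high on the textual fault and low on its size and direction.

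**What to change.** In the Tuning paragraph of SAP 7.9.1, restrict the AUROC grid search to b and the training hyperparameters. Before outcome modelling begins, state one primary (l, w) pair in days for the short-term model and one for the long-term model. Choose them for intended clinical use, with input from the Steering Committee (CIP 5.3), and apply them identically to every algorithm and comparator. Report other pairs in a descriptive sensitivity table, which would also reveal any lag between AF and care. The documents give no basis for particular values, so none is proposed here.

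The cost is SAP wording and one advance decision on two pairs. Sample size and data collection do not change. The reported AUROC may be lower than the grid maximum: in the short-term illustration, fixing (30,30) instead of taking the grid winner lowered mean validation AUROC by 0.155 (time-varying), 0.069 (mixed) and 0.014 (stable).

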13.1 Statistical Study Design Considerations

The DEFINE AFib study is a prospective, observational post-market clinical study intended to leverage machine learning to evaluate the association between complex patterns of device-detected AF and elevated healthcare utilization, reduced QoL and specific clinical outcomes in patients with a LINQ ICM. These data will improve our understanding of how data from the LINQ ICM can be used to guide the management of AF patients. The DEFINE AFib study is not designed to be powered and no specific hypotheses will be tested. However, the sample size was determined with the goal of having an adequate number of endpoint events to develop risk prediction models that can have incremental clinical benefit beyond what is available as standard of care.

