13.3.1 Hypothesis

No formal statistical hypotheses will be tested for this objective. Rather, the goal will be to determine whether a risk prediction model can be developed from device-collected measurements that can has adequate sensitivity and specificity to be of use in a clinical setting.

Analysis Methods

Various risk prediction models will be developed and compared to each other. The model(s) with best predictive power will be selected. The input data of these models might be composed of values (original or derived) collected by LINQ ICMs, and the output of the model will be the risk of patient having a AF-related HCU in the future. The model may also account for attributes of patients' medical histories, including CHA2DS2-VASc scores, individual components of CHA2DS2-VASc scores and any other medical

Page 36 of 48

[figure not shown]

history information provided by the patient at enrollment. The predictive value of the model will generally be assessed against the predictive power of any clinical tools available at the time of model development. If additional predictive tools become available at the time of model development, those tools can be integrated into the development of the model and the value of the model will reflect the incremental benefit provided above and beyond the available clinical tools.

Endpoint: Confirmed healthcare visit in the inpatient hospital, outpatient hospital, clinic/office, emergency department, or other care location (including remote visits) where AF was the reason or suspected reason for healthcare interaction.

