7.5 Adjustments for Multiple Comparisons

No adjustment for multiple comparisons will be made. This is a single arm study, where the goal in the primary objective is to develop predictive models and not perform hypothesis testing.

Revision [2.0]

Page 13 of 25

Demographic and Other Baseline Characteristics

Descriptive statistics will be used to summarize baseline and demographic characteristics. For categorical variables (e.g. sex), counts and percentages will be employed, while for continuous variables (e.g. age), means, standard deviation, quartiles, minimum, and maximum will be provided. These statistics will be provided for all enrolled subjects and also stratified by LINQ device model.

7.7 **Treatment Characteristics**

This section does not apply since no treatment effect is being measured in this study.

Interim Analyses 7.8

An interim analysis was initially planned to be performed when there were observed 500 thousand patient-days OR when it had been 16 months since 1st enrollment (whichever comes first). Due to a transition from CIP V3 to CIP V4 (and associated app infrastructure changes) near the time of the planned interim analysis, in addition to slow initial enrollment, the interim analysis timeline was updated to occur within 2 years of the 1st enrollment. The objective of this interim analysis will be to reassess the assumptions and determine if the sample size or follow-up duration of the study needs to be adjusted. Based on the interim analysis, details of how the study objectives will be analyzed (e.g., types of statistical models used) are subject to revision.

Evaluation of Objectives

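### The model is to be contrasted with existing clinical tools, but the readable SAP plans no confidence interval for the difference and does not fix the comparator before test results are seen

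*SAP*

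**What the plan says.** Protocol section 13.3.1 says that the predictive value of the primary model will "generally be assessed against the predictive power of any clinical tools available at the time of model development". If further tools appear by then, they may be built into the model, and "the value of the model will reflect the incremental benefit provided above and beyond the available clinical tools". SAP section 7.9.1 (Testing) uses softer words for the same comparison: "For each outcome, the performance of the risk prediction models will be presented in contrast to the performance of comparable clinical practices".

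The interval method stands just before that sentence. AUROC, sensitivity, specificity, NPV and PPV are computed for the models, and "Bootstrapping will be used to compute 95% CIs for these performance metrics". No interval for a model-minus-comparator difference is mentioned, and none for the comparator.

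For each endpoint there are two kinds of model, "one focusing on short term predictions and other on long term predictions", with an open list of algorithms. Neither horizon is marked as the leading one. The readable primary-objective text names no comparator; CHA2DS2-VASc appears there only as a possible model input.

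The test set is reserved until the models have been trained and validated, and missing-data choices must also precede its use. No such rule covers the comparator. Protocol section 13.1 adds: "The DEFINE AFib study is not designed to be powered and no specific hypotheses will be tested". SAP section 7.5 adds: "No adjustment for multiple comparisons will be made".

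**The concern.** The documents make the gain over existing tools part of how the model's value will be described, but the planned output does not measure the uncertainty of that gain. Model and tool are scored on the same test patients, so their AUROC estimates are correlated. The standard error of the difference depends on that correlation, which two separate CIs do not show. A reader given two AUROCs, even each with its own CI, could not tell whether the gain is established.

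The comparator is bounded only by what is available at model development. If it, or the horizon, were settled after test results were known, the reported gain could be biased upwards.

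**Working it through.** **1. The plan's own figures.** From Protocol section 13.1 and SAP section 6: 80/0.05/10 = 160 and 80/0.02/10 = 400 events. The 320 to 800 events for an algorithm are twice these (the factor 2 is inferred). 5,000 × 21% = 1,050 AF-related events, and 1,050 × 50% = 525 with half the cohort complete. All reproduce. They concern model convergence; the plan states no precision for the contrast.

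**2. Size of the test set.** SAP section 7.9.1 puts 20% of patients in the test set.
- Half complete: 2,500 × 20% = 500 patients, 525 × 20% = 105 events.
- Full data: 5,000 × 20% = 1,000 patients, 1,050 × 20% = 210 events.

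I treat each event as one patient with one score. If the 21% applied only to the 2,350 patients with any utilization, there would be about 494 events, hence about 49 to 99 in the test set, and wider intervals.

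**3. What separate CIs leave open.** With m event and n non-event patients, the Hanley-McNeil variance of an AUROC A is [A(1−A) + (m−1)(Q1−A²) + (n−1)(Q2−A²)]/(mn), where Q1 = A/(2−A) and Q2 = 2A²/(1+A). For the difference, SE = √(s1² + s0² − 2·r·s1·s0), where r is the correlation of the two AUROC estimates.

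Assume AUROCs 0.75 (model) and 0.70 (tool), m = 105, n = 395. Then s1 = 0.0294 and s0 = 0.0308. The separate CIs are 0.692 to 0.808 and 0.640 to 0.760, and they overlap. The 95% CI for the difference of 0.05 is:
- r = 0: −0.033 to 0.133
- r = 0.5: −0.009 to 0.109
- r = 0.7: 0.004 to 0.096
- r = 0.9: 0.023 to 0.077

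The same two CIs fit a difference interval that includes 0 and one that excludes it.

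**4. How often the two summaries agree.** Simulated test sets used binormal scores, score correlation 0.5 and DeLong variances. AUROCs and correlation are assumptions.

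| AUROCs | Events / test patients | Paired 95% CI excludes 0 | Separate 95% CIs do not overlap |
|---|---|---|---|
| 0.70 vs 0.60 | 105 / 500 | about 90% | about 28% to 30% |
| 0.70 vs 0.60 | 210 / 1,000 | over 99% | about 80% |
| 0.75 vs 0.70 | 105 / 500 | about 40% | about 2% |

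In the first row the SE of the difference is about 0.03 paired and 0.042 unpaired. At score correlation 0.3 that row becomes 79% against 32% to 35%; at 0.7, about 99% against 24% to 26%.

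Hand check of the first row with Hanley-McNeil and r = 0.5: s1 = 0.0308, s0 = 0.0321, SE = √(0.0308² + 0.0321² − 0.0308 × 0.0321) = 0.0315. Paired: Φ(0.10/0.0315 − 1.96) = Φ(1.21) = 0.89. Non-overlap needs a difference above 1.96 × (0.0308 + 0.0321) = 0.123: Φ((0.10 − 0.123)/0.0315) = Φ(−0.73) = 0.23. This is lower than the simulated figure because the Hanley-McNeil SEs are slightly larger.

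**5. Choosing the comparator after seeing results.** Assume that the model and k tools all have true AUROC 0.70, with r = 0.5, and that the most favourable contrast is reported. The chance that the lower limit of even a paired 95% CI exceeds 0 is 2.5% for k = 1, 4.5% for k = 2, 6.3% for k = 3 and 9% for k = 5. With 105 events the mean false gain is 0.012, 0.018 and 0.025 for k = 2, 3 and 5.

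**The case against.** The study disclaims hypothesis testing and power. The stated goal in Protocol section 13.3.1 is a model whose sensitivity and specificity suffice for clinical use, and those metrics do get CIs. The comparison is worded softly in both documents, and the incremental-benefit sentence follows a conditional about additional tools. All of this stands: no superiority claim is defined. It removes the need for a test, but not for an interval on a gain that the documents say they will assess.

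The comparator is also tied to tools available at model development, and the test set is held back until the models are final. That narrows the gap but does not close it, since no text fixes the comparator before test results are known. Pages that are blacked out or missing might name one.

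A reader might infer more than the documents support:
- That the plan will decide by comparing point estimates or by non-overlap of CIs. It states neither rule; the second serves above only to show what separate CIs convey.
- That separate CIs miss most real gains. This depends on the scenario: non-overlap occurs about 80% of the time for 0.70 vs 0.60 with 210 events, and about 90% for 0.75 vs 0.60 with 105.
- That a worthless model would look better half the time. The 50% figure belongs to a model equal to the tool, which may still be useful.
- That four contrasts are in play (two horizons by two algorithms), giving an 80% chance that at least one looks favourable when model and tool are equal. The Testing text can be read as two final models for the endpoint. With correlation 0.5 between two contrasts the chance is 1 − (1/4 + arcsin(0.5)/(2π)) = 2/3.
- That CHA2DS2-VASc is a weak comparator and AF burden a strong one. The documents give no discrimination for either.

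**Conclusion.** The point holds as a gap in how the planned contrast is reported. The readable text promises a comparison with existing tools, provides intervals only for single metrics, and leaves the comparator open until after test results could be known. At the planned test-set size the consequence can be large or modest. For an assumed gain of 0.10 AUROC, a paired interval and separate CIs agree fairly well with 210 events and poorly with 105. For a gain of 0.05 with 105 events, even the paired interval excludes 0 only about 40% of the time, which is itself worth showing.

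These sizes rest on assumed AUROCs and correlations, and on one score per patient. The SAP scores every patient on every day and does not state the bootstrap's resampling unit. Resampling days as if independent would make the intervals too narrow.

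**What to change.** In SAP section 7.9.1, Testing:

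1. Add the paired difference in AUROC (model minus comparator), computed on the same test patients and patient-days, with a 95% CI from a bootstrap that resamples whole patients. Describe the model as better than existing tools only to the extent that this interval supports it. No formal hypothesis test is needed.
2. Before the test set is opened, fix the comparator, the lead horizon and the lead model for this contrast, using non-test data only. Label the other contrasts as supportive.

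The choice of comparator is the sponsor's. If AF burden alone is chosen, state that the contrast is then between a complex and a simple use of LINQ data, since burden is itself a LINQ measurement.

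The cost is SAP wording and a few lines of code, with no new data or patients. The small downside is that some apparent gains would be reported as not established.
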